Date	9/27/18
Title	Are we supporting the apex during hysterectomy for pelvic organ
	prolapse?
Principal Investigator	[name], MSc
Sub-Investigators	[name]; [name]; [name],
	MD; [name], DO; [name]
Research Specialist	[name], MS
Department	Department of OB/Gyn, Division of Urogynecology and
	Reconstructive Pelvic Surgery
Hatton #	17-091

Purpose of Study:

- To determine whether gynecologic surgeons at a large community hospital are already meeting the recently recommended best practice of supporting the vaginal apex at time of hysterectomy for pelvic organ prolapse.
 - Primary Aim: To determine the proportion of patients undergoing hysterectomy for the indication of pelvic organ prolapse having concurrent apical suspension such as: McCall's culdoplasty, Uterosacral Ligament Suspension, Sacrospinous Ligament Fixation, Abdominal Sacrocolpopexy, or Robotic Sacrocolpopexy.
 - Secondary Aims: Identify characteristics of surgeons not meeting the recommended best practice including their training, location of operation, operative times, concurrent procedures and estimated blood loss.

Hypothesis or Research Question

 We hypothesize that fewer than 10% of patients having hysterectomy for pelvic organ prolapse will not undergo concurrent apical support, being defined as McCall's Culdoplasty, Uterosacral Ligament Suspension, Sacrospinous Ligament Fixation or Robotic/Abdominal Sacrocolpopexy.

Background

The prevalence of pelvic organ prolapse (POP) in the United States is estimated to be between 40-50% with an anticipated increase over the next several decades¹⁻³. Approximately 300,000 women undergo surgeries to repair POP in the United States every year⁴. Following pelvic reconstructive surgery, recurrence rates of symptomatic prolapse range between 6-30%⁵⁻⁹. This number has changed in recent years to favor a lower recurrence rate. This change in recurrence rate may be attributed to the efforts of pelvic surgeons in restoring proper levels of support during repairs.

Our understanding of pelvic anatomy and its support has been significantly improved over recent decades, with many researchers reporting on details and mechanics previously not understood. A landmark article by DeLancey¹¹ proposed a now widely accepted model

outlining the support of the pelvic organs, ordering specific aspects of support from level one to level three. This model then helped drive continued efforts in improving approaches and outcomes for reconstructive surgery.

Historically, a majority of women having pelvic reconstructive surgery would undergo anterior and posterior colporrhaphy for repair of their prolapse¹². This was considered an appropriate standard of care. More recently, the integral relationship between loss of apical support and both anterior and posterior compartment defects has been demonstrated¹³⁻¹⁵. Then, in 2013, Eilber reported on the outcomes of vaginal prolapse surgery among female medicare beneficiaries¹⁶. They investgated a 10 year period including over 3,200 women who had undergone pelvic reconstructive surgery. They found that women having concurrent apical support procedures were significantly less likely to have recurrence of prolapse than those women who had no apical support performed.

In November 2017, the American College of Obstetricians and Gynecologists released a new practice bulletin outlining the current standard of care for the treatment of women with pelvic organ prolapse¹⁷. In this bulletin, they state that a hysterectomy alone is not adequate treatment for pelvic organ prolapse, and further that any woman having a hysterectomy for pelvic organ prolapse should undergo a concurrent apical suspension procedure as a standard of care. The question then arises, what proportion of our patients currently receive this standard of care?

Our purpose therefore is to investigate the proportion of patients undergoing hysterectomy for the indication of pelvic organ prolapse at a TriHealth facility who receive a concurrent apical support procedure as recommended by ACOG, which includes: McCall's Culdoplasty, Uterosacral Ligament Suspension, Sacrospinous Ligament Fixation and Robotic/Abdominal Sacrocolpopexy.

Research Plan

Study Design

Retrospective Descriptive Study

Setting for the study

 A retrospective chart review will be performed on TriHealth EPIC platform of patients of TriHealth who underwent hysterectomy for pelvic organ prolapse at any of the affiliated TriHealth hospitals between October 2012 and October of 2017.

Participants

- Study population: All women 18 years of age or older, who underwent hysterectomy for pelvic organ prolapse, performed at a TriHealth facility between October 2012 and October 2017.
- o A chart review will be performed on all patients identified.

- Inclusion criteria
 - Adults 18 years of age or older
 - Underwent hysterectomy for pelvic organ prolapse, performed at a TriHealth facility between October 2012 and October 2017
- Exclusion criteria
 - Age < 18 years old
 - Pelvic Organ Prolapse was not an indication for their surgery
 - Surgery performed by a physician of Cincinnati Urogynecology Associates.
- Sample size
 - Given the retrospective nature of this study, a sample size calculation is not indicated. However, estimating the number of charts that may be available can be garnered from internal reports on department activity. Between October 2012 to October 2017, 792 hysterectomies took place at a Trihealth Facility for the indication of prolapse. Excluding those performed by a physician of the Cincinnati Urogyn Associates group, there are approximately 194 cases eligible for review. With this in mind, in order to provide for potential differences in case number during the years within the study period, we request permission to review up to 250 cases.

Data Collection

- Each chart will be reviewed and the following data will be collected or extrapolated:
 - General demographic data name, date of birth, age, race, parity, BMI
 - Select comorbidities (connective tissue disorders, history of chronic constipation, history of chronic cough)
 - Operative details Date of surgery, concurrent procedures performed, type of apical support, length of procedure, facility or location of procedure performed, estimated blood loss, reported intra-operative complications, primary surgeon, whether FPMRS or General OB/GYN.

Intervention or experimental aspect of the study

- No intervention will occur as part of this study.
- There are no potential risks to the study population by any aspect of the study.

Statistical Analysis

 Given the descriptive nature of this study, limited statistical analysis will be performed. The proportion of patients who did not have concurrent apical support procedures performed will be calculated. Furthermore, the proportion of patients who had various postoperative outcomes (as defined above) will be calculated and compared to previous published literature.

Ethical Considerations

Informed consent

 Since this is a retrospective study, waivers of Informed Consent and Authorization will be requested.

• Privacy information

- Extensive efforts will be made to ensure and maintain participant confidentiality. All identifying information will be maintained in a secure area at all times. All communication between staff members regarding participant data will occur via the Subject ID number only. However, identifying information will be retained in the original/source documents.
- The Excel spreadsheet will be stored on a password protected, encrypted
 TriHealth computer for ten years following study closure, and then purged.

Cost/Budget

• This study will incur no cost to the institution, the participants, or the investigators.

Estimated Period of Time to Complete Study		
Estimated Period of Time to Complete Study		
When will study begin?	January 2018	
Protocol Development	2 weeks	
Completed		
Admin Review Time	2 weeks	
IRB Approval	3 weeks	
Data collection	8 weeks	
Data analysis	2 weeks	
Presentation development	2 weeks	
(if applicable)		
Manuscript Development	4 weeks	
(if applicable)		
Journal submission process	4 weeks	
(if applicable)		
Study closure	2 weeks	

• When and how will results be disseminated?

The results will be disseminated at one of our division research meetings and potentially as a presentation at a national meeting.

References

- 5. Dallenbach P. To mesh or not to mesh: a review of pelvic organ reconstructive surgery. Int J Womens Health 2015; 7:331-343

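### Does open wording in the primary aim and closed wording in the hypothesis leave the primary measure undefined?

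*Combined protocol and SAP*

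**What the plan says.** The combined document describes the primary measure in four places.

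- **Purpose of Study, Primary Aim:** the proportion of patients "having concurrent apical suspension such as" five named procedures; in full, "having concurrent apical suspension such as: McCall's culdoplasty, Uterosacral Ligament Suspension, Sacrospinous Ligament Fixation, Abdominal Sacrocolpopexy, or Robotic Sacrocolpopexy".
- **Hypothesis or Research Question:** fewer than 10% of patients "will not undergo concurrent apical support, being defined as" the same five procedures, with robotic and abdominal sacrocolpopexy joined by a slash.
- **Background, closing purpose statement:** the proportion of patients who "receive a concurrent apical support procedure as recommended by ACOG, which includes" the same five again.
- **Statistical Analysis:** "The proportion of patients who did not have concurrent apical support procedures performed will be calculated", with no list and no cross-reference.

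Two other places bear on the point. The Background, summarising the practice bulletin, says that these women "should undergo a concurrent apical suspension procedure as a standard of care". Data Collection lists "concurrent procedures performed, type of apical support" among the operative details, without limiting either item to set categories.

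**The concern.** The study's main result is a single proportion, so the rule that decides who counts as supported is central. The aim's wording admits apical suspensions beyond the five, while the hypothesis's wording shuts them out. No sentence says which takes precedence or how an unlisted suspension is to be coded.

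The direction of the effect is known. The closed list can only raise the unsupported proportion, which works against the study's own hypothesis; the open list can only lower it. If unlisted suspensions turned up, the proportion would have two defensible values, and the choice could be made after the counts were seen. The same classification could feed the secondary aim, to "Identify characteristics of surgeons not meeting the recommended best practice", so a surgeon might be labelled as falling short because of list wording alone.

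**Working it through.** **Comparing the texts.** The aim, the hypothesis and the purpose statement name the same five procedures; none is added or dropped. Their readings part only for a patient whose sole apical procedure is unlisted.

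The purpose statement is weak evidence for an open list. Its list follows directly on the reference to the ACOG recommendation and can be read as spelling that set out. The conflict therefore rests on the aim against the hypothesis.

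Between those two, the hypothesis alone offers a definition, and the term it defines is apical support. The analysis sentence uses that term and, like the hypothesis, is framed as the absence of support. The aim uses a different noun, suspension. On an ordinary reading, the defined term keeps its meaning when the analysis sentence repeats it.

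**Sensitivity.** The plan states no calculated figure to reproduce. The 194 (expected eligible cases) and the 250 (most charts requested), both under Sample size, are chart counts. Let *n* be the number of cases, *x* the unsupported count under the open reading, and *k* the number of patients with only an unlisted suspension. The documents do not give *k*, so its values here are assumptions.

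- Open proportion = *x*/*n*; closed proportion = (*x* + *k*)/*n*; shift = *k*/*n*.
- Largest count *m* with *m*/*n* below 10%: at *n* = 194, *m* = 19 (19/194 = 9.79%; 20/194 = 10.31%). At *n* = 250, *m* = 24 (24/250 = 9.60%; 25/250 = 10.00%, which is not fewer than 10%).
- The answer changes only if *x* ≤ *m* and *x* + *k* ≥ *m* + 1, that is, *m* + 1 − *k* ≤ *x* ≤ *m*.

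| *k* (assumed) | Shift, *n* = 194 | Answer changes if *x* is | Shift, *n* = 250 | Answer changes if *x* is |
|---|---|---|---|---|
| 0 | 0 | never | 0 | never |
| 1 | 0.52 points | 19 | 0.40 points | 24 |
| 3 | 1.55 points | 17–19 | 1.20 points | 22–24 |
| 5 | 2.58 points | 15–19 | 2.00 points | 20–24 |

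For scale, the exact (Clopper-Pearson) 95% interval around 19/194 runs from 6.0% to 14.9%. A result that close to 10% would not settle which side of the line the underlying proportion lies on, under either reading.

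**Can the data carry either reading?** Yes. Type of apical support and concurrent procedures are both abstracted without restriction. An analyst can list every type found, see whether *k* is zero, and produce both counts without returning to the charts.

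**The case for a change.** The best case for a change is that the analysis sentence is where the measure should be made operational, and it neither defines its term nor points back to the hypothesis. An abstractor who meets an unlisted suspension has no written rule. With one headline proportion, five such patients could turn 15/194 (7.73%) into 20/194 (10.31%). Fixing one definition, adding a code for other suspensions and naming one count as primary would cost almost nothing. The status of a conventional laparoscopic sacrocolpopexy could be settled at the same time.

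Part of this stands. The two wordings do differ, there is no express statement of precedence, and matching the aim to the hypothesis would be tidier.

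The rest does not show that the plan as written gives a wrong or worse result. The five patients are assumed, and a reversal also needs the open count to fall in a narrow band. The laparoscopic question comes from outside the documents, which never mention that route. The surgeon-level effect cannot be traced, because the plan has no rule for turning patient results into a surgeon group. Choosing a reading after seeing the counts would be hard to hide in any report that tabulates type of support, as a descriptive study would be expected to do.

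**Conclusion.** No change to the plan is needed. The inconsistency is one phrase in the primary aim, set against an explicit definition in the hypothesis whose term the analysis sentence repeats. Following that definition is the natural course, and it is also the stricter one for the study's own hypothesis.

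The effect is 0.52 points per unlisted-only patient at 194 cases and 0.40 at 250. The number of such patients is unknown and may be zero. The 10% figure is an expectation in a retrospective descriptive study, with no test or significance level attached, so no formal decision turns on crossing it.

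This conclusion rests on two assumptions: that abstractors record the actual procedure, as Data Collection provides, and that unlisted suspensions are few or absent. If the second proved wrong, the recorded types would show it and either count could be reported from the same data.

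### Operative time and blood loss are listed as traits of surgeons who omit apical support, yet both totals include the suspension when it is done

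*Combined protocol and SAP*

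**What the plan says.** Under Purpose of Study, the secondary aim is to "Identify characteristics of surgeons not meeting the recommended best practice including their training, location of operation, operative times, concurrent procedures and estimated blood loss". The practice in question is set by the primary aim, which counts patients "having concurrent apical suspension such as: McCall's culdoplasty, Uterosacral Ligament Suspension, Sacrospinous Ligament Fixation" or one of the other listed procedures. A surgeon is therefore classified by a step taken within the same operation.

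Data Collection lists among the operative details "concurrent procedures performed, type of apical support, length of procedure", then facility, then "estimated blood loss, reported intra-operative complications, primary surgeon, whether FPMRS or General OB/GYN". There is one entry for length and one for blood loss, and nothing says that the suspension's share is recorded separately. Type of apical support is listed apart from concurrent procedures.

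Statistical Analysis opens with "Given the descriptive nature of this study, limited statistical analysis will be performed". For apical support it then states only that "The proportion of patients who did not have concurrent apical support procedures performed will be calculated". It gives no analysis for the secondary aim, no rule for when a surgeon counts as not meeting the practice, and no tabulation by type of support.

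**The concern.** The aim asks who the surgeons are that leave the apex unsupported. Training and location can answer that, because they are not produced by the decision to suspend. Operative time and blood loss are different: they are results of the operation, and the suspension is part of it whenever it is done. Two surgeons alike in all else, one suspending and one not, would differ in operative time by the length of the suspension.

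At stake is the reading of a secondary table. A difference that comes partly from the missing step could be reported as a feature of the surgeon, for example that those who do not follow the recommendation operate faster.

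**Working it through.** The plan has no figure of its own to reproduce: it gives no suspension time, standard deviation, significance level or power. The check is a comparison of definitions, followed by arithmetic on stated assumptions.

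**1. Which listed characteristics contain the suspension?**

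| Characteristic in the aim | How it is collected | Contains the suspension? |
|---|---|---|
| Training | FPMRS or general OB/GYN | No |
| Location | Facility | No |
| Operative time | One length per procedure | Yes, when done |
| Blood loss | One estimate | Yes, when done |
| Concurrent procedures | List of procedures; apical type is a separate item | Only if also counted here; not stated |

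**2. Size of the overlap.** Let m be the minutes a suspension adds, and let pA and pB be the support rates in two surgeon groups that are otherwise identical.

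- By case (supported versus unsupported): overlap = m.
- By surgeon group: overlap = (pA − pB) × m.

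Assumed values, none from the documents: m = 15 to 45 minutes; pA = 95%; pB = 60%, or 30% as a more extreme case.

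- (0.95 − 0.60) × 15 = 5.25 and × 45 = 15.75, so 5 to 16 minutes.
- (0.95 − 0.30) × 15 = 9.75 and × 45 = 29.25, so 10 to 29 minutes.

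The same formula applies to blood loss. The overlap between surgeon groups is 35% or 65% of whatever net blood loss the suspension adds, an amount that the documents do not give.

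For concurrent procedures, a suspension that is counted adds exactly 1 per supported case, so 0.35 or 0.65 procedures per case between the surgeon groups. If it stays in its own field, the overlap is 0.

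**3. Could it be seen at this study's size?** Sample size puts the eligible cases at about 194. The hypothesis is "We hypothesize that fewer than 10% of patients having hysterectomy for pelvic organ prolapse will not undergo concurrent apical support". At that 10% bound, 194 × 0.10 = 19.4, so about 19 unsupported and 175 supported cases. As an illustration only, 4,000 studies per setting were simulated with identical surgeons, an assumed SD of 40 minutes and a Welch t-test at 5%:

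| Minutes added by the suspension | Nominally significant |
|---|---|
| 0 | 5% |
| 10 | 16% |
| 20 | 50% |
| 30 | 84% |
| 40 | 98% |

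The plan specifies no such test. The table shows only that a purely mechanical difference could be visible in these data.

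**4. Could surgeons be compared within unsupported cases instead?** That would remove the overlap but leave about 19 cases. With the 95% and 60% rates and 10% omission overall, let x be the cases of the lower-support group: 0.40x + 0.05(194 − x) = 19.4, so 0.35x = 9.7 and x = 27.7. Unsupported cases are then 0.40 × 27.7 = 11 in that group and 0.05 × 166.3 = 8 in the other, before any split by surgeon. That is too few to be useful.

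**The case against.** The strongest reply is that this is a descriptive chart review. The aim names variables to describe, the analysis section writes no contrast by support status, and no claim about efficiency is made. It is true that the contrast is implied by the aim and not specified. But the aim cannot be met without setting these surgeons or their cases beside the others, and calling time and blood loss characteristics of surgeons is already the misattribution, with or without a test. Type of apical support and primary surgeon are collected, so the right tables can be made; the plan does not say that they will be.

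A reader might also infer more than the documents support:

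- **That all three operative items overlap by definition.** Data Collection lists type of apical support apart from concurrent procedures. The protocol also calls the suspension concurrent, so the count is ambiguous, but overlap there is conditional.
- **That omitters must show less blood loss and fewer procedures.** Neither direction is shown. Background describes anterior and posterior colporrhaphy as the historical repair, so surgeons who leave out the suspension may do other repairs instead.
- **That these variables carry no information.** Mixed is not empty. What else was done when the apex was not supported is worth describing.

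The minutes and support rates are indeed assumptions with nothing in the documents to anchor them.

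**Conclusion.** The point holds for operative time and estimated blood loss: as collected, a contrast by support status mixes the suspension's own contribution with any difference between surgeons. For concurrent procedures it holds only if the suspension is counted among them.

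The size cannot be found from the documents. The minutes given above rest on the assumed suspension times and support rates, and on groups that are otherwise identical. The surgeon-group figures also need a grouping rule that the protocol does not give.

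The consequence is confined to how one descriptive secondary aim is read. The primary proportion is unaffected, as are training and location. It would go too far to say that the secondary aim is uninformative, or that the plan commits to a misleading comparison. A cheap change of wording and tables is justified.

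**What to change.** - Base the surgeon characteristics on training, location and case volume, the last counted from the primary-surgeon field.
- Report operative time and estimated blood loss as case-level descriptions of the operation, by support status and type of suspension, and say that they are not surgeon traits.
- State that concurrent procedures are counted without the apical procedure. Keep the others, such as colporrhaphy, as description.
- Do not add a surgeon comparison within unsupported cases.

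The cost is rewording one aim and laying out its tables from fields already listed; no new data are needed. The investigators give up operative time and blood loss as surgeon-level characteristics, and some strata by type of suspension will be small.

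### The Purpose and Background ask about present practice, but the only planned primary result is a 2012–2017 average, with no estimate for a recent period

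*Combined protocol and SAP*

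**What the plan says.** The Purpose of Study is to learn whether surgeons "are already meeting the recently recommended best practice of supporting the vaginal apex". The Background, after describing the November 2017 practice bulletin, asks "what proportion of our patients currently receive this standard of care". Both are questions about the present.

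The Primary Aim asks for the proportion of hysterectomies for prolapse with concurrent apical suspension and names no time point. The hypothesis reads: "We hypothesize that fewer than 10% of patients having hysterectomy for pelvic organ prolapse will not undergo concurrent apical support". It names no time point either.

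The inclusion criterion sets the window: "Underwent hysterectomy for pelvic organ prolapse, performed at a TriHealth facility between October 2012 and October 2017". The Sample size section expects that "there are approximately 194 cases eligible for review". It foresees differences between years only in the number of cases, not in the rate of apical support.

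The Statistical Analysis section says "Given the descriptive nature of this study, limited statistical analysis will be performed", and then: "The proportion of patients who did not have concurrent apical support procedures performed will be calculated". It plans no breakdown by year and no estimate for a recent period. Data Collection records "Date of surgery, concurrent procedures performed, type of apical support, length of procedure", so calendar time is on the data sheet but is given no role in the analysis.

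**The concern.** A proportion pooled over five years is the average of the yearly rates, weighted by yearly case numbers. It describes present practice only if the rate was about constant. The Background gives some reason to ask whether it was: it describes a move from colporrhaphy towards apical support and cites a 2013 outcomes report, early in the window, that favoured apical support.

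If practice did change, an undated pooled figure set beside the 10% in the hypothesis could be read as a statement about what patients receive now, when it reflects a mixture of earlier and later practice. As planned, the study would report nothing that lets a reader tell the difference.

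**Working it through.** The plan contains no calculated figure to reproduce. The question is how far a pooled rate can differ from a recent one, and how precisely a recent one can be estimated.

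**Inputs from the protocol.** About 194 eligible cases; a window of about five years; 10% in the hypothesis.

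**Assumptions (not in the protocol).** Cases spread evenly: 194/5 = 38.8, taken as 39, 39, 39, 39 and 38. Yearly no-support rates follow a straight line on the logit scale between assumed first-year and last-year values.

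**Step 1. Pooled against recent rate.** Pooled rate = Σ(nᵢ × pᵢ)/194.

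| Assumed no-support rate | Years 1 to 5 (%) | Expected events | Pooled | Last two years (n = 77) | Last year |
|---|---|---|---|---|---|
| Falling | 20.0, 13.8, 9.3, 6.1, 4.0 | 7.80 + 5.37 + 3.61 + 2.39 + 1.52 = 20.69 | 20.69/194 = 10.7% | (2.39 + 1.52)/77 = 5.1% | 4.0% |
| Rising | 4.0, 5.7, 8.2, 11.5, 16.0 | 1.56 + 2.24 + 3.19 + 4.49 + 6.08 = 17.56 | 17.56/194 = 9.1% | (4.49 + 6.08)/77 = 13.7% | 16.0% |

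In each row the pooled point value lies on the other side of 10% from the recent one. With a constant rate, say 8% every year, the two agree.

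**Step 2. Sampling error of the pooled values.** Normal approximation, p ± 1.96√(p(1 − p)/194):
- 10.7%: 6.3% to 15.0%
- 9.1%: 5.0% to 13.1%

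Both intervals include 10%, so neither pooled result would be firm evidence of falling short or of complying.

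**Step 3. Uneven case numbers.** Take yearly rates of 20, 16, 12, 8 and 4%. Even numbers give a pooled 12%. With case shares of 30, 25, 20, 15 and 10%, the pooled rate is 6.0 + 4.0 + 2.4 + 1.2 + 0.4 = 14.0%. With the shares reversed it is 2.0 + 2.4 + 2.4 + 2.0 + 1.2 = 10.0%. The yearly rates are the same in all three.

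**Step 4. Precision of a recent-period estimate.** Half-width at 10%, 1.96√(0.1 × 0.9/n): 9.4 points for n = 39, 6.7 for n = 78, 4.2 for n = 194. Exact (Clopper–Pearson) 95% intervals:
- one year, 3/39 = 7.7%: 1.6% to 20.9%
- two years, 6/78 = 7.7%: 2.9% to 16.0%
- whole window, 16/194 = 8.2%: 4.8% to 13.0%

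Rounding the two-year events in Step 1 to whole cases, 4/77 gives 1.4% to 12.8% and 11/77 gives 7.4% to 24.1%. These also include 10%.

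**Step 5. What a trend model would add.** A logistic model in calendar year, fitted to the Step 1 rates through the expected information, gives last-year intervals of 1.4% to 10.8% (falling) and 8.4% to 28.3% (rising). Power to detect the slope, two-sided at 5%, is about 68% and 51%. The model rests on about 21 and 18 events, assumes a smooth trend and ignores clustering by surgeon. It does not settle the 10% question either.

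**The case against.** The strongest reply is that the pooled proportion is exactly what the operative text asks for. *Currently* appears only in a Background question; the statement of purpose that follows it, the Primary Aim and the hypothesis do not use it. *Already* can fairly mean before the bulletin, which is dated November 2017, a month after the window closes. On that reading the study is a pre-bulletin baseline and a five-year average is a reasonable target. This stands, and it is why the pooled figure should remain the primary result. It does not remove the mismatch with the Background question, nor the chance that an undated figure is read as current.

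A second reply is that the change in practice is historical. The colporrhaphy statement cites a 1999 paper, and the anatomical evidence cited for the apex dates from 2006, 2008 and 2013. This also stands: nothing in the protocol shows that practice changed at these hospitals within the window.

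Two stronger readings are tempting. A reader might infer that the study would wrongly declare surgeons compliant or non-compliant. The documents do not support that: the plan states no decision rule or test at 10%, the trends in the working are assumed and large (a five-fold fall, a four-fold rise), and every interval there for the two scenarios includes 10%. A reader might also infer that a trend model should carry the conclusion about current practice. With so few events, a smooth-trend assumption and no allowance for surgeon clustering, that goes further than the data can bear.

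Lastly, date of surgery is also needed to establish eligibility, so recording it does not show that a time analysis was intended and forgotten.

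**Conclusion.** The point holds in a limited form. The Purpose and the Background question concern present practice; the one planned primary result is an average over October 2012 to October 2017. That average validly answers the Primary Aim, and it equals the recent rate only if practice was stable.

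The size of any discrepancy cannot be derived, because the documents give no yearly rates or case counts. Under the assumed trends the pooled and last-year values differ by about 7 points in either direction (10.7% against 4.0%; 9.1% against 16.0%). Under a constant rate they do not differ at all. This is a gap in reporting and interpretation that is cheap to close, not a flaw that invalidates the primary estimate.

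**What to change.** In the Statistical Analysis section:

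1. Keep the pooled proportion as the primary result and label it as covering October 2012 to October 2017 wherever it is reported.
2. Using date of surgery, report the number and proportion without apical support for each 12-month period, and for one recent period fixed before the data are examined, such as the last 24 months. Give each an exact 95% confidence interval and present them as descriptive.
3. Limit any statement about what patients currently receive to the recent-period estimate and its interval. Otherwise word the conclusion as applying to the whole window.
4. A trend model may be added as a descriptive supplement. It should not be the basis for the conclusion, and a non-significant slope should not be taken as evidence of stable practice.

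The cost is a short table from data already being collected, with no extra charts. The drawback is width: about 9 points either side at 10% for a single year and about 7 for two years, against about 4 for the whole window. The recent-period result may therefore not settle on which side of 10% practice lies, and the report should say so.
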